2.1. Study Objectives, Endpoints, and Estimands

Primary objective

Assess change in (1) PRO as measured by EORTC-QLQ-C30 collected via smartphone-based application and (2) physical activity as measured by wearable device in Japanese patients with HR+/HER2- advanced breast cancer receiving below treatment as first or second line setting:

1. *Palbociclib plus endocrine therapy (Group 1) or*
2. *Endocrine monotherapy (Group 2)*

NOTE: The study is not intended to compare outcomes between the two groups as the primary objective.

Secondary objectives

The following research objectives will be addressed separately for both Group 1 and 2. When associations for group 1 and 2 are similar, the group 1 and 2 will be pooled.

- *Assess the association between change in EORTC-QLQ-C30 and physical activity versus investigator-reported adverse event (AE)*
- *Assess the association between change in EORTC-QLQ-C30 and physical activity versus patient-reported symptom as measured by PRO-CTCAE collected via smartphone-based application*
- *Assess the association between change in EORTC-QLQ-C30 versus change in physical activity*
- *Assess the association between change in EORTC-QLQ-C30 and physical activity versus disease progression*
- *Assess the feasibility of collecting physical activity data with the wearable device in Japanese patients with advanced breast cancer*
- *Assess patient's treatment satisfaction (collected as a single item via smartphone-based application)*
- *Evaluate concordance and discordance between investigator-assessed AE versus PRO-CTCAE*
- *Characterize patients with HR+/HER2- ABC initiating each group treatment (eg, baseline patient demographics and clinical characteristics)*

The following research objectives will be addressed Group I only.

- *Describe dosing patterns (eg, dose reduction, dose interruptions, cycle delay)*

CCI

2.2. Study Design

The study is a prospective, multicenter, observational study to evaluate PRO (Health related QOL) and physical activity using smartphone-based application and wearable device in Japanese patients with HR+/HER2- ABC.

Patients will be enrolled into either palbociclib plus endocrine therapy group (Group 1) or endocrine monotherapy group (Group 2) based on the discretion of the treating physician under routine clinical practice. Total target number of patients is approximately one-hundred in this study (About 50 patients in each group).

[figure not shown]
Enrolled patients will download a smartphone-based application for electronic PRO (ePRO), be provided access to and trained on the use of the application to complete baseline, daily, weekly, and cycle-based assessments for 6 cycles (24 weeks). In addition, enrolled patients will be provided with wearable device and requested to wear the device at all-times, except of while bathing and sleeping, for 6 cycles (24 weeks).

In this study, one cycle is defined as follows;

- In Group 1 (palbociclib plus endocrine therapy), palbociclib is administered for 3 consecutive weeks followed by 1 week off treatment to comprise one cycle of 4 weeks. If palbociclib is temporarily interrupted (eg, due to adverse event) and the start of the next cycle is delayed, the duration of one cycle may exceed 4 weeks, then, the observation period may exceed 24 weeks.
- In Group 2 (endocrine monotherapy), one cycle is defined as 4 weeks.

Participation in this study is not intended to change the routine treatment that patients receive as determined by their prescribing clinicians; all treatment decisions and type and timing of disease monitoring are at the discretion of the treating physician. No additional visits to the clinic will be required for the purposes of the study.

Figure 1. Study Design

It is anticipated that all data collection for this study will occur over a 18-month period (from the first patient's first visit to the last patient's end of study assessment),

Planned patient enrollment duration: 12 months

Planned data collection for an individual patient: 6 cycles (24 weeks*)

*In Group 1, if palbociclib is temporarily interrupted (eg, due to adverse event) and the start of the next cycle is delayed, the duration of one cycle may exceed 4 weeks, then, the observation period may exceed 24 weeks.

3. ENDPOINTS AND BASELINE VARIABLES: DEFINITIONS AND CONVENTIONS

3.1. Primary Endpoint(s)

- *EORTC-QLQ-C30 (Global health status scale)*
 - The EORTC-QLQ-C30 is a 30-item questionnaire to evaluate cancer patients' QOL, and it's composed of five multi-item functional subscales (physical, role, emotional, cognitive, and social functioning), three multi-item symptom scales (fatigue, nausea/vomiting, and pain), a global quality of life (QOL) subscale, and six single item symptom scales assessing other cancer-related symptoms (dyspnea, sleep disturbance, appetite loss, constipation, diarrhea, and the financial impact of cancer). The questionnaire employs 28 4-point Likert scales with responses from "not at all" to "very much" and two 7-point Likert scales for global health and overall QOL. Responses to all items are then converted to a 0 to 100 scale. For functional and global QOL scales, higher scores represent a better level of functioning/QOL. For symptom-oriented scales, a higher score represents more severe symptoms. A 10-point or higher change in scores from baseline is considered clinically significant.
 - Change of scores from baseline at each cycle
 - Scores at each cycle
- *Physical activity metrics (Sedentary time)*

All the physical activity metrics variables will be analyzed with "WEARFILTERED" (ie. "Wear" = TRUE.)

- Average of a week, which includes 5 or more days of wearing 10 hours or longer during a day except for bedtime.
- Change from baseline at each week
- Sedentary time (sedentary time means) at each week

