14. LIMITATIONS OF THE RESEARCH METHODS

Considering the nature of real-world observational study, the study has the potential for missing, inaccurate, or incomplete data. Especially, as this study require patients to self-report outcomes and behavior, completeness and accuracy of reporting can be a concern. The limitations of the observational nature can result in methodological challenges in attributing causality to outcomes. Hence, this study is intended for hypothesis generation as opposed to hypothesis confirmation.

The patient selection and the diagnostic or monitoring procedures are those applied per the usual treatment paradigm of the treating physician and not dictated by the protocol.

Heterogeneous patient populations could make the interpretation of the outcomes difficult.

As this study will collect PRO data via smartphone-based application, participating patients must own and have regular access to smartphone; thus, the study population may not be representative of the ABC population, which may include technology- or mobile device-naïve patients.

As the data collection period for each patient is 6 months, feasibility of ePRO and wearable device (ie, ePRO data entry and wearing period) can be a concern.

Although it is easily understood by general public, Steps is not well validated with wrist watches and sometimes underestimated. Therefore, Sedentary time is also evaluated to assess the impact of ABC treatment on patients' physical activity.

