3.2. Secondary Endpoint(s)

- *Other EORTC-QLQ-C30 subscales*
- *Other physical activity metrics (Steps, MVPA time)*
 - The main variables collected and/or derived from wearable device are shown in Table 2.
- *Adverse events and any laboratory abnormalities (Type, incidence, severity, seriousness and relationship to study medications)*

- *PRO-CTCAE (Fatigue and General pain)*
 - *The PRO-CTCAE is a PRO measurement system that includes a library of questions that measure symptomatic adverse events from the patient perspective. Seventy-eight symptom terms that are common in oncology clinical trials can be evaluable with PRO-CTCAE, and each of symptom terms is assessed relative to one or more distinct attributes, including frequency, severity, and/or interference with usual or daily activities. Responses are provided on a five-point Likert scale.*
- *Disease progression*
- *Patient treatment satisfaction*
 - *Treatment satisfaction will be evaluated with single item question (eg, “How satisfied are you with your current breast cancer treatment?”). Responses are provided on a five-point Likert scale.*
- *Palbociclib treatment (including dose, dose reduction, dose interruption, cycle delay)*

Table 2. Physical activity metrics variables from wearable device

Variables	Definition
Steps	Total estimated steps taken per Date.
Wear minutes	Total minutes of algorithmically detected “wear time”
Sedentary behavior	Number of total minutes defined as Sedentary Behavior as defined using the Staudenmayer '15 technique.
Light activity	Number of total minutes spent in Light activity category as defined using the Staudenmayer '15 technique.
Moderate activity	Number of total minutes spent in Moderate activity category as defined using the Staudenmayer '15 technique.
Vigorous activity	Number of total minutes spent in Vigorous activity category as defined using the Staudenmayer '15 technique.
MVPA	Total estimated number of minutes of Moderate or higher (moderate to vigorous) physical activity per Date as calculated using the Staudenmayer '15 technique.
Calories	Total estimated calories per Date as calculated using the “Hildebrand Nonlinear” technique.
MET	Total estimated METs per Date as calculated using the “Hildebrand Nonlinear” technique.

Note: All the physical activity metrics variables will be analyzed with “WAKEWEARFILTERED” (ie. “Wear” = TRUE. Excludes minutes that fall within a sleep period.)

CCI

[REDACTED]

[REDACTED]

[REDACTED]

[REDACTED]

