6.1.2. Change in “Sedentary time” (Sedentary time means)

6.1.2.1. Main Analysis

Physical activity metrics are averaged at weekly basis. As primary analysis of physical activity, change in “Sedentary time” from baseline is summarized at weekly basis, separately by groups. Baseline values are the average number of those measured between enrollment and the day before treatment start (the baseline observation period).

For patients with less than 4 days of measurements before the treatment start, the measurements from the first 4 days are used.

Least squared mean and the 95% CI of the score for each cycle will be estimated using mixed effect model for repeated measures. The covariates included in the model will be group, cycle (categorical variable), group -and-cycle interaction term, week of each cycle, and baseline score.

The same analysis will be performed for the population excluding patients who had less than 4 days of measurements prior to the start of treatment.

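### Primary sedentary minutes are not adjusted for time worn, so any shift in daily wear from baseline would be reported as a change in sedentary time

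*SAP*

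**What the plan says.** SAP Table 2 (section 3.2) gives the sedentary metric as a count: "Number of total minutes defined as Sedentary Behavior". Wear minutes are a separate row of the same table: "Total minutes of algorithmically detected" wear time.

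SAP 3.1 turns the count into a weekly value and sets the qualifying rule: "Average of a week, which includes 5 or more days of wearing 10 hours or longer during a day except for bedtime". The rule selects weeks and days; it does not scale the minutes that remain.

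SAP 6.1.2.1 makes the primary contrast a change from baseline: "change in “Sedentary time” from baseline is summarized at weekly basis, separately by groups". The repeated-measures model contains "group, cycle (categorical variable), group -and-cycle interaction term, week of each cycle, and baseline score". Wear time is not among the terms.

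The documents describe the minute filter in two ways. SAP 3.1 applies WEARFILTERED (worn minutes). The note under Table 2 applies WAKEWEARFILTERED (worn minutes outside a sleep period).

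**The concern.** Under either filter, a sedentary minute is recorded only if the watch is on. The weekly value therefore reflects two things: the share of worn time spent sedentary, and the amount of time worn. Only the first is behaviour. If patients put the watch on later or take it off earlier as the study goes on, recorded sedentary minutes fall with no change in what they do. If baseline wear is short and later wear is longer, the minutes rise.

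At stake is one of the study's two primary results: the mean change in sedentary time and its 95% interval. SAP 6.2.2 runs the same analysis for steps and MVPA time, and also uses the activity metrics in the comparisons by adverse event and PRO-CTCAE symptom. SAP 6.2.3 correlates them with change in QLQ-C30. Wear could differ between patients who are well and unwell, so the same mechanism can enter there.

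**Working it through.** **Inputs.** The plan states no expected value, SD or precision for sedentary time, and Protocol 12.1 sets the sample size on practical grounds, so there is no figure to reproduce. Protocol 9.1 gives 20 to 80 patients per group. Sedentary share, wear hours and SD are not in the documents; the values below are assumptions.

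**1. Structure.** Let W be mean worn minutes per day and p the sedentary share of worn time. Then recorded minutes S = p × W, and change = p1·W1 − p0·W0. With behaviour unchanged (p1 = p0 = p), change = p × (W1 − W0). This is zero only if mean wear is unchanged.

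**2. Size per hour of drift.** 0.50 × 60 = 30 min; 0.60 × 60 = 36 min; 0.75 × 60 = 45 min. With constant behaviour:

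| Mean wear, baseline to follow-up | p = 50% | p = 60% | p = 75% |
|---|---|---|---|
| 14 h to 13 h | −30 | −36 | −45 |
| 14 h to 12 h | −60 | −72 | −90 |
| 14 h to 10 h | −120 | −144 | −180 |
| 10 h to 14 h | +120 | +144 | +180 |

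Every wear level in the table meets the 10-hour minimum.

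**3. Masking.** Suppose the share truly rises from 60% to 70% while wear falls from 14 h to 12 h. Baseline: 0.60 × 14 × 60 = 504 min. Follow-up: 0.70 × 12 × 60 = 504 min. The reported change is 0. On a fixed 14-hour day (840 min) it would be 0.10 × 840 = +84 min.

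**4. Against sampling error.** The 95% half-width is t(0.975, n−1) × SD / √n. For an assumed SD of change of 60 to 120 min, this is 28 to 56 min at n = 20 and 13 to 27 min at n = 80. One hour of drift (30–45 min) exceeds the half-width at n = 80 and is of similar size at n = 20. Two hours (60–90 min) exceed it at both.

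**5. Simulation.** 4,000 runs with n = 80, mean share constant at 0.60, and mean wear falling by about 1 h from about 14 h. The mean change in raw minutes was about −35 min/day (SD about 68), and its 95% interval excluded zero in 99.6% of runs. The mean change in sedentary share was about 0 percentage points, and its interval excluded zero in 4.9% of runs, as it should.

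**6. Do the rules in SAP 3.1 and 6.1.2.1 prevent this?** The 10-hour, 5-day rule removes short days but leaves wear above 10 h free to vary. The repeat analysis in SAP 6.1.2.1 drops patients with fewer than 4 pre-treatment days; it addresses number of days, not hours per day. SAP 6.1.2.1 states no hours-per-day rule for baseline, and the roughly 4-day baseline recommended in Protocol 10 cannot meet a 5-day rule. Baseline and follow-up wear may thus be selected differently.

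**The case against.** The strongest reply is that the missing term matters only if mean wear shifts, and nothing in the documents shows that it will.

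- The endpoint is a within-patient change in weekly averages, so stable wearing habits largely cancel. This stands. A reader might contrast a valid 10-hour day with a valid 15-hour day and quote a 180-minute error (5 h × 36 min). That compares single days and is not the size of any error in the endpoint.
- Patients are asked to wear the watch at all times except bathing and sleeping (Protocol 9.1 and 10). Staff check wearing status at visits about every 30 days and are alerted after 4 weeks without wear. SAP 6.2.6 reports data counts and time to wearable failure. These controls limit drift, but none of them measures or corrects hours per day.
- Protocol 14 says that "feasibility of ePRO and wearable device (ie, ePRO data entry and wearing period) can be a concern". A reader might take this as the sponsor expecting shorter daily wear. It more naturally concerns how long patients keep using the device, and it does not mention hours per day.
- The per-day unit is partly inferred, because the sedentary row of Table 2 omits the per-date wording used for steps and MVPA. This is a gap in definition, but no reading of the row brings in wear time.
- Parts of SAP 3.3, 5.2, 6.1.2.2 and 6.3 are redacted or not shown. A supplementary wear-adjusted analysis cannot be excluded, so the criticism is confined to the visible primary definition and model.
- Adjustment has its own problems. Under the wake-wear filter, wear in a compliant patient approximates time awake, which illness or treatment may alter. Conditioning on it can remove real change. A percentage also assumes that unworn time resembles worn time. This stands, and is why adjustment should be supportive.
- The study is descriptive (Protocol 12.1, SAP 5.1), so no test-based decision is at risk. This limits the consequence, but the mean change and its interval are the study's main product.

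**Conclusion.** The point holds in a conditional form. The visible primary definition and model contain no scaling or covariate for wear time, and a minimum-wear rule does not supply one. Any difference in mean daily wear between baseline and follow-up is therefore reported as a change in sedentary time, at 30–45 min/day per hour of drift if the sedentary share is 50–75%. That the difference passes through follows from the definition; its size rests on assumed shares and hours.

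A reader might infer that the primary result is biased, or that minutes should be replaced as the primary metric. The documents support neither. They give no wear hours, so the occurrence, direction and size of bias are unknown. Replacing the metric would change what is being estimated. It would also need a protocol amendment if treated as a major change to a primary endpoint (Protocol 12.5, SAP 2). And it would be open to post-hoc criticism, since SAP version 1.1 (April 2023) post-dates the planned end of data collection (28 February 2023).

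**What to change.** 1. Reconcile the WEARFILTERED statement in SAP 3.1 with the WAKEWEARFILTERED note under Table 2, so that the wear denominator is defined. If worn sleep is counted, each hour asleep with the watch on can add up to 60 min.
2. Keep unadjusted minutes as the stated primary form.
3. In SAP 6.1.2.1 add a wear-adjusted analysis to be read alongside it. Either add baseline and weekly mean wake-wear minutes as covariates, or analyse sedentary time as a percentage of wake-wear minutes. With the covariate form, report least-squares means with weekly wear set equal to baseline wear; means taken at the observed averages would leave the average drift in.
4. Tabulate mean wear minutes at baseline and each week by group, over the days that enter the endpoint. A flat table would largely settle the question.
5. Use the covariate form for steps, which cannot be a share of minutes, and either form for MVPA.

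**Cost.** SAP wording, a derived variable from data already collected, and a little more analysis. With the primary form unchanged, the amendment clause should not be triggered. The adjusted analysis conditions on post-baseline wear, which may partly reflect real change in time awake, so it must be labelled supportive. If it is added after results have been seen, it should be labelled as such.

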5.3. Methods to Manage Missing Data

In the primary analysis, missing data will be excluded from the analysis at each measured point. For calculating scores of EORTC-QLQ-C30 and PRO-CTCAE, missing data will be handled according to the guidance of the developers.

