6.2.2. Physical activity metrics

- ✓ The same analysis for other physical activity metrics (steps, MVPA time) is performed as for Sedentary time.
- ✓ The similar analyses of each physical activity metrics, as same as that for EORTC-QLQ-C30, are performed to assess the associations.

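### SAP 3.1 sets its 10-hour wear rule for the week, not the day, and baseline has no hours rule, so short-wear days can bias change in sedentary time either way

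*SAP*

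**What the plan says.** The only wear-time criterion is in SAP 3.1, under sedentary time: "Average of a week, which includes 5 or more days of wearing 10 hours or longer during a day except for bedtime". SAP 6.1.2.1 adds only that "Physical activity metrics are averaged at weekly basis". Protocol 12.5.1 says the same and has no wear-time rule.

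SAP Table 2 (section 3.2) defines the sedentary metric as "Number of total minutes defined as Sedentary Behavior". Steps and MVPA are likewise totals per date. Wear minutes are a listed device variable, but they are neither a denominator for the endpoint nor a covariate in the SAP 6.1.2.1 model. SAP 6.2.2 carries the approach over: "The same analysis for other physical activity metrics (steps, MVPA time) is performed as for Sedentary time".

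Baseline in SAP 6.1.2.1 is the average of measurements from enrollment to the day before treatment. With fewer than 4 days before treatment, the first 4 days of measurement are used. A further analysis omits patients with fewer than 4 pre-treatment days. These rules count days and do not mention hours of wear.

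**The concern.** The rule screens weeks. It does not say which days of a qualifying week enter the mean. Because the daily value is a total of worn minutes, a day worn for 4 hours gives a low sedentary total whatever the patient did, and gives low steps and MVPA for the same reason.

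Sedentary time is one of the two primary endpoints, and its change from baseline is the primary result. If short days stay in, part of that change reflects how long the watch was worn. Two programmers working from the same sentence could also produce primary results tens of minutes per day apart. If patients wear the device less when unwell (an assumption), the artefact would also reach the adverse-event comparisons at Cycles 1 and 3 and the correlations with EORTC-QLQ-C30.

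**Working it through.** The documents give no figure for this point, so there is nothing to reproduce. The check has two parts.

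**Could short days be removed elsewhere in the plan?**
- SAP 3.1: a week qualifies with "which includes 5 or more days of wearing 10 hours or longer". The number of other days it may hold is 7 − 5 = 2.
- SAP 3.1 and the Table 2 note: the filters drop minutes, not days. Section 3.1 names a wear filter. The Table 2 note names a wake-and-wear filter ("Excludes minutes that fall within a sleep period"). The two differ, which matters for how the 10 hours are counted.
- SAP 5.3: "missing data will be excluded from the analysis at each measured point". For this endpoint the measured point is the week, so a short day inside a week with a value is not addressed.
- SAP 6.1.2.1: the covariates are group, cycle, their interaction, week of cycle and baseline. Wear minutes are not among them.

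No text excludes the short days, and no text says that they are kept.

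**How large is the effect if they are kept?**

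Assumptions, not in the documents: true behaviour is constant; W = hours worn on a valid day; s = share of worn time that is sedentary; w = 4 hours on a short day.

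Daily sedentary minutes = 60 × s × hours worn. On valid days this runs from 60 × 0.55 × 13 = 429 to 60 × 0.65 × 15 = 585 min.

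Fall in a 7-day mean with k short days = k × 60 × s × (W − w) / 7.

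| Case | W = 13 h, s = 0.55 | W = 15 h, s = 0.65 |
|---|---|---|
| One 4-hour day | 60 × 0.55 × 9 / 7 = 42 | 60 × 0.65 × 11 / 7 = 61 |
| Two 4-hour days | 85 | 123 |

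Fall in a 4-day baseline with one 4-hour day = 60 × s × (W − w) / 4. At W = 14 h:
- s = 0.5: 60 × 0.5 × 10 / 4 = 75 min/day
- s = 0.7: 60 × 0.7 × 10 / 4 = 105 min/day

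**Direction, at W = 14 h and s = 0.60** (504 min on a full day, 144 min on a 4-hour day):
- Short day in the week only: (6 × 504 + 144) / 7 = 453, so the change reads 453 − 504 = −51.
- Short day in baseline only: (3 × 504 + 144) / 4 = 414, so the change reads 504 − 414 = +90.
- One in each: 453 − 414 = +39.

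**A true change can reverse sign.** Let the sedentary share rise from 0.60 to 0.65 at 14 h. The true change is 546 − 504 = +42 min/day. With one 4-hour day in the week (156 min), the observed change is (6 × 546 + 156) / 7 − 504 = −14 min/day.

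**What a day filter leaves behind.** If wear on every day falls from 14 h to 10 h at s = 0.60, all days still qualify and the mean still falls by 60 × 0.60 × 4 = 144 min/day.

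**The case against.** The strongest reply is that the SAP is silent, not wrong. The sentence in 3.1 can be read as an average made up of five or more days worn at least 10 hours, which is already a mean over valid days. That reading is possible, and under it the weekly bias disappears. It does not cover baseline, where no hours rule is stated under any reading.

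A reader might go further than the text allows in three ways.
- **That the plan scores unworn days as zero.** Nothing says so. The filters keep only worn minutes, and a day without any has nothing to analyse.
- **That falling adherence must show as falling sedentary time.** This holds only while at least 5 days still qualify, because below that the week has no value. Short baseline days push the change upward. The protocol's limitations section says only that wearing the device over 6 months may be a feasibility concern and gives no adherence pattern.
- **That a day filter cures wear dependence.** The 144 min/day example shows that it does not.

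Two further objections stand in part. Dropping short days may remove days when patients felt ill, so the exclusion may be informative. The study is also descriptive (SAP 5.1), so no error rate or decision depends on this. The estimated change is nevertheless the primary result, and both its size and its sign depend on the rule.

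**Conclusion.** The concern holds in this form: the wear criterion is attached to the week, nothing excludes days under 10 hours from the weekly mean, and baseline has no hours-per-day rule. On the literal reading, one 4-hour day moves a weekly mean by about 42 to 61 min/day and two by 85 to 123. One 4-hour day in a 4-day baseline moves baseline by about 75 to 105 min/day. The bias in either average is downward, so the bias in change from baseline can go either way.

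These sizes rest on the assumed wear hours, sedentary shares and 4-hour short day. How often short days occur is unknown, so they describe an affected patient-week or baseline and not a group mean. The documents do not support saying that the plan deliberately keeps short days, or that the result is biased toward improvement.

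**What to change.** In SAP 3.1 and 6.1.2.1, state that a valid day has 10 or more hours of waking wear, and that the weekly value is the mean over valid days only, calculated when the week has at least 5. Apply the same day filter to the baseline days, and to steps and MVPA. Name one minute-level filter in both 3.1 and the Table 2 note, so that waking wear is counted the same way throughout.

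Baseline must be included. In the example with one short day in each period, filtering only the weekly values would move the spurious change from +39 to +90 min/day.

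The cost is a few sentences and a filter on wear minutes that are already derived. Partial-wear days go unused, and some patients will have fewer usable baseline days, so the SAP should say whether its 4-day baseline count means valid days. Reporting the number of excluded days by week would show whether the exclusion follows illness. Dependence on wear time among days of 10 hours or more needs separate treatment.
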